3 OVERALL STUDY DESIGN AND PLAN

3.1 Study design

Study AC-080A201 is a prospective, multi-center, double-blind, double-dummy, randomized, placebo- and active-reference, parallel group, Phase 2 dose-finding study with ACT-132577 in subjects with essential hypertension (grade 1 and 2).

Approximately 640 subjects will be enrolled into the study, in order to have at least 540 subjects randomized in the 6 following groups in a 1:1:1:1:1 ratio; placebo, 5 mg ACT-132577, 10 mg ACT-132577, 25 mg ACT-132577, 50 mg ACT-132577, lisinopril 20 mg. At least 420 subjects are expected to complete the trial.

The study consists of the following study periods:

Pre-screening:

Subjects without a confirmed diagnosis of mild-to-moderate hypertension are offered the possibility of having their BP measured (at trough if subjects are on anti-hypertensive treatment) with an automated office BP device before entering the screening period. These subjects must sign the "confirmation of diagnosis" Informed Consent Form (ICF) before BP measurement. If hypertension is confirmed then the subject will be proposed to enter the study.

Screening:

Screening lasts up to 72 h starting from the signature of the "study" ICF until the run-in period eligibility decision.

Run-in period (Period I)

Period I is a single-blind (SB) placebo period of 4 to 6 weeks starting at the end of Visit 1 and ends at Visit 4 Randomization (after completion of the baseline 24-h ABPM recording on the last dose of SB study treatment [placebo]).

The run-in period is 4 weeks for anti-hypertensive treatment naïve subjects at Screening (Visit 1). Visit 1 is combined with Visit 2.

The run-in period is 6 weeks for subjects on anti-hypertensive treatment at Screening (Visit 1) including a 2-week wash-out period for anti-hypertensive treatment. In such a case, anti-hypertensive treatment must be discontinued (according to its label) at Visit 1, if there is no contra-indication to stop it.

Essential hypertension Protocol AC-080A201 Version 3 30 May 2016, page 36/112

Confidential

Treatment period (Period II)

Period II is a double-blind (DB) treatment period of 8 weeks which starts at Visit 4 / Randomization with the first dose of DB study treatment and ends at Visit 7 / Part 2 (after completion of the 24-h ABPM recording on the last dose of DB study treatment).

Withdrawal period (Period III)

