8.1 Screening and run-in periods

Screening lasts up to 72 h, starting with the signature of the "study" ICF and lasting until the Visit 1 eligibility assessments (i.e., eligibility to enter the run-in period) are completed.

The run-in period takes place 4 to 6 weeks prior to Day 1 (Visit 4 / Randomization) and starts with the Screening visit (Visit 1) and ends with the Randomization visit. The run-in period is an SB placebo treatment period; the study staff must not inform the subjects about the treatment they are receiving during the run-in period.

The run-in period is 4 weeks for anti-hypertensive treatment naïve subjects at Screening (Visit 1). Visit 1 is combined with Visit 2.

The run-in period is 6 weeks for subjects on anti-hypertensive treatment at Screening (Visit 1), including a 2-week wash-out period for anti-hypertensive treatment. In such a case, anti-hypertensive treatment must be discontinued (according to label) at Visit 1 if there is no contra-indication to stop it.

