2 STUDY DESIGN AND FLOW

2.1 Study design

Study AC-080A201 is a prospective, multi-center, double-blind, double-dummy, randomized, placebo- and active-reference, parallel group, Phase 2 dose-finding study with ACT-132577 in subjects with essential hypertension (grade 1 and 2).

Approximately 1000 subjects are enrolled into the study, in order to have at least 540 subjects randomized in the 6 following groups using a 1:1:1:1:1:1 ratio: placebo, 5 mg ACT-132577, 10 mg ACT-132577, 25 mg ACT-132577, 50 mg ACT-132577 and lisinopril 20 mg. At least 420 subjects are expected to complete the trial. There are no stratification factors.

The study consists of the following study periods:

Screening

The screening period starts with the signature of the “study” informed consent form and lasts until Visit 1. During this period study assessments (e.g., laboratory test) are performed to determine whether the subject is eligible for the study.

Run-in period (Period I)

Period I is a single-blind (SB) placebo period of 4 to 6 weeks starting at Visit 1 and ends at Visit 4 / Randomization (after completion of the baseline 24-hour ambulatory blood pressure monitoring [ABPM] recording on the last dose of SB study treatment [placebo]).

The run-in period lasts 4 weeks for anti-hypertensive treatment naïve subjects.

The run-in period lasts 6 weeks for subjects on anti-hypertensive treatment including a 2-week wash-out period for anti-hypertensive treatment. The anti-hypertensive treatment must be discontinued (according to its label) at Visit 1, if there is no contraindication to stop it.

Treatment period (Period II)

Period II is a double-blind (DB) treatment period of 8 weeks which starts at Visit 4 with the first dose of DB study treatment and ends at Visit 7 at the first dose of SB withdrawal treatment.

Withdrawal period (Period III)

Period III is a SB placebo period of 2 weeks, which starts at Visit 7 with the first administration of first placebo dose (withdrawal [WD] study treatment) and ends at Visit 8 (WD-End-of-Treatment [EOT]).

Follow-up period

The follow-up period, including follow-up telephone call, or follow-up visit only for women of childbearing potential to perform the pregnancy test at the site, starts after the last dose of SB WD study treatment (placebo) and ends at 30–33 days after the last dose of the DB treatment.

End-of-Study (EOS)

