5.2.2 Baseline disease characteristics

Baseline disease characteristics include:

- Duration of essential hypertension (years) at Screening [see Section 11.8 for definition]
- Treatment for hypertension ongoing at Screening (Y/N), as collected in the **Treatment of Hypertension - Summary** eCRF.
- Mean trough sitting diastolic blood pressure (SiDBP) at Screening as measured by OBPM
- Mean trough sitting systolic blood pressure (SiSBP) at Screening as measured by OBPM

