The null hypothesis of ‘no dose-response’ will be rejected if at least one of the six Multiple Contrast Tests (MCTs) has a multiplicity adjusted p-value < 0.05. All statistically significant models (i.e., with an adjusted p-value < 0.05) are fitted in the Mod step and for each model Akaike’s Information Criterion (AIC) is calculated. The smaller the value of AIC (= model deviance + 2 times the number of model parameters), the better the fit. The analysis will be performed using the R-package *DoseFinding* [Bornkamp 2016]. The basic R-code is:

```
library(DoseFinding)
doses <- c(0, 5, 10, 25, 50)
candMod <- Mods(linear = NULL, linlog = NULL, quadratic = -0.005, emax = 50,
               sigEmax = c(50, 0.5), logistic = c(50, 50), doses = doses,
               direction="decreasing")
MMfit <- MCPMod(dose=dose, resp=resp, data=DF, addCovars=~base, models =
candMod, Delta=3)
```

In the Mods function call the candidate models are specified, together with the assumed direction of the effect (decreasing for change from baseline in blood pressure). In the call to the MCPMod function, DF is a data frame with objects dose, resp (for response), and base (for the baseline value) and Delta is a target difference vs placebo (Delta=3 for DBP; Delta=5 for SBP). The object *MMfit* will be summarized to obtain the MCP test, parameter estimates, target dose and AIC. These elements will go in a summary table. The object will be plotted to display the fitted dose-response curves.

Subgroup analyses based on MCP-Mod can be performed by fitting the selected model by subgroup using the *fitMod* function for which the basic R-code is:

```
MMfit1 <- fitMod(dose=dose, resp=resp, data=DF[DF$subg==1,], addCovars=~base,
model=MMfit$selMod)
MMfit2 <- fitMod(dose=dose, resp=resp, data=DF[DF$subg==2,], addCovars=~base,
model=MMfit$selMod)
```

As a supportive analysis to MCP-Mod, change from baseline to Week 8 in DBP and SBP will also be analyzed in an ANCOVA model using the Dunnett test.

```
proc mixed data=dset;
  class treat;
  model outcome=treat base;
  lsmeans treat / adjust=Dunnett diff=control('0') cl;
  where week=8 and treat in (0,1,2,3,4);
run;
```

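### Adding antihypertensive treatment at Screening as a covariate is a cheap, small precision gain; leaving it out is not an error

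*SAP*

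**What the plan says.** Protocol 3.1 ties the run-in to treatment status at Visit 1: "The run-in period is 6 weeks for subjects on anti-hypertensive treatment at Screening (Visit 1) including a 2-week wash-out period for anti-hypertensive treatment". Protocol 8.1 gives the other group less time: "The run-in period is 4 weeks for anti-hypertensive treatment naïve subjects at Screening (Visit 1".

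The status is collected. SAP 5.2.2 lists "Treatment for hypertension ongoing at Screening (Y/N" among the baseline disease characteristics, and SAP 10.4.2 summarizes those by treatment group for the FAS and PPS.

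The status is not used in allocation. SAP 2.1 states: "There are no stratification factors".

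Nor is it used in analysis:
- The primary fit in SAP 9.2 begins "MMfit <- MCPMod(dose=dose, resp=resp, data=DF, addCovars=~base, models". Its data frame holds dose, "resp (for response), and base (for the baseline value", so baseline SiDBP is its only covariate.
- The supportive ANCOVA in the same section uses "model outcome=treat base".
- The mixed models in SAP 9.3 add week and its interactions with treatment (where included) and baseline.
- The logistic models in SAP 9.4 and the ABPM ANCOVAs in SAP 10.7 and 10.8 use treatment and the relevant baseline only.
- Prior treatment is not among the subgroups in SAP 8.

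The SAP gives no reason for leaving it out.

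**The concern.** Previously treated subjects qualify at Visit 1 with DBP of at least 90 mmHg at trough on their drugs, then stop them. Naïve subjects meet the same threshold untreated. The two groups may therefore follow different blood pressure courses after randomization, even from the same baseline value. If they do, part of the residual variance in the Week 8 change is explained by an item already in the database, and an unstratified trial will carry some chance imbalance in it. A baseline covariate would recover that precision for the dose-response test and for the fitted curve that informs the choice of Phase 3 doses.

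**Working it through.** **Inputs from the documents.** 70 per group in the PPS, a 4 mmHg maximum difference and SD 9 mmHg (Protocol synopsis and 11.5.1); SD 7.4 mmHg in the previous macitentan study (Protocol 11.5.1); two-sided alpha 0.05; five arms in the dose-response test; candidate models and true curves from Appendix 15.2 of the sample size re-estimation SAP.

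**Inputs that must be assumed.** The share p on treatment at Screening (30%, 50%, 70%), and the gap g in mean Week 8 change between treated and naïve subjects that remains after adjustment for baseline SiDBP (0–4 mmHg). The documents give neither.

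**Reproducing the plan's figure.** Rebuilding the two-sided multiple contrast test (optimal contrasts for six models, doses 0/5/10/25/50 mg, four true curves with maximum effects 5, 4.5, 4.5 and 4 mmHg, df = 5n − 5) gives average power at SD 9 of 80.8%, 90.3% and 95.2% with 47, 63 and 79 per group. Protocol Table 4 assigns these sizes 80%, 90% and 95%, so it reproduces.

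**Starting point.** With 70 per group, SD 9 and a 4 mmHg maximum for all four curves, power is 90.4%, 84.9%, 87.9% and 86.8%, averaging 87.5%. This is below the figure of over 95% in Protocol 11.5.1, which does not reproduce from these curves. Only the change from the starting point matters here.

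**Adding the covariate.** Variance removed: R² = p(1 − p)g²/SD². New residual SD = SD × √(1 − R²), with one further df spent. For p = 0.5, g = 4, SD 9: R² = 0.25 × 16/81 = 4.9%, and the SD falls to 8.775.

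| Gap g (mmHg) | R², p = 0.5 | Power, p = 0.5 | R², p = 0.3 or 0.7 | Power, p = 0.3 or 0.7 |
|---|---|---|---|---|
| 1 | 0.3% | 87.6% | 0.3% | 87.6% |
| 2 | 1.2% | 87.9% | 1.0% | 87.8% |
| 3 | 2.8% | 88.4% | 2.3% | 88.2% |
| 4 | 4.9% | 89.1% | 4.1% | 88.8% |

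At SD 7.4 and p = 0.5, 96.6% rises to 96.7%, 96.9%, 97.2% and 97.6%.

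**Cost if it explains nothing.** The lost df alone leaves power at 87.5%. Estimating the coefficient inflates the variance of a contrast by about 1/342 = 0.3% (342 = 350 − 5 − 1 − 1 − 1). In the table an R² of 0.3% is worth about 0.1 point, so the loss is about 0.1 point, to 87.4%. The table does not subtract this cost.

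**Break-even.** Setting R² = 1/342 with p = 0.5 and SD 9: g² = 81/(342 × 0.25) = 0.95, so g is about 1 mmHg.

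**Chance imbalance.** For p = 0.5, the SD of the difference in share between two arms of 70 is √(2 × 0.25/70) = 8.5 percentage points. At g = 4 this moves a dose-placebo difference by 0.085 × 4 = 0.34 mmHg (1 SD). The variance of that difference is 2 × 81/70 = 2.31, and √(0.049 × 2.31) = 0.34. The two calculations give the same quantity: the shift is the part of the standard error that R² describes.

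**The case against.** The case for leaving the models alone has several parts, and most of it stands.

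- **Validity.** A reader might infer that an unstratified trial with no adjustment has a biased or invalid primary test. The documents do not support that. With random allocation, omitting a baseline covariate neither biases the comparison nor inflates type I error. Selection into the PPS is a separate question that this covariate does not settle.
- **Two different populations.** A reader might take the 4- and 6-week run-ins as unequal preparation. Protocol 3.2 explains that the extra 2 weeks are a wash-out added to the same 4-week run-in. Both groups must meet the same Visit 4 range (SiDBP 90 to below 110 mmHg, Protocol 4.3), and subjects still on antihypertensives at randomization are excluded from the PPS (SAP 6). A difference in later course is possible but not shown.
- **Size.** Share and gap are both assumed. Baseline SiDBP may already carry part of the information, and a 4 mmHg residual gap would equal the whole drug effect used for sample size.
- **Imbalance as a further harm.** The 0.34 mmHg shift is tempting to add to the power gain. It is the same gain in other units.
- **Cost.** It is small but not zero, and the net gain may be nil. The ANCOVA, mixed and logistic covariates are set in Protocol 11.3.2.4 and 11.3.3, so this is a declared change.
- **Visibility.** A marked imbalance would show in the baseline tables. That reveals it but does not recover the precision.

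What remains is that the item is collected, plausibly prognostic and nearly costless to use.

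**Conclusion.** This is a cheap improvement, not an error. At SD 9 and 70 per group, the covariate changes average power by between about −0.1 and +1.6 points over gaps of 0–4 mmHg and shares of 30–70%. At SD 7.4 with a 50% share, the gain is at most 1.0 point. These figures rest on the assumed share and gap, on treating the planning SD as the residual SD after baseline adjustment, and on a gap that is the same in every arm. The downside is bounded and very small; the upside is modest and undocumented. The documents do not support any claim that the primary result would be wrong without it.

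**What to change.** Before unblinding:

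1. Add antihypertensive treatment ongoing at Screening (Y/N) as a fixed covariate to the primary fit (`addCovars=~base+priortrt`), the ANCOVAs and the mixed models. In the mixed models, give it a by-week term wherever baseline has one (SAP 9.3).
2. State the LS-means weighting over its two levels, for example observed margins. In the linear models without a treatment interaction this moves the arm levels but not the differences between arms.
3. Treat it as optional in the logistic models. SAP 9.4 carries predicted probabilities into MCP-Mod, and the covariate and its weighting slightly change what those probabilities mean.
4. List the change in SAP 4.1.

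The cost is one df in the primary model, about 0.1 power point if the item is not prognostic, and a few lines of SAP text. Randomization, sample size and data collection stay as they are. If unblinding has already taken place, report the adjusted model only as a labelled sensitivity analysis.

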# read data frame lsm from xpt file
est <- lsm$ESTIMATE # LSMeans
C <- lsm[,c("COV1","COV2","COV3","COV4","COV5")] # covariance matrix
doses <- c(0,5,10,25,50)
MMfit <- MCPMod(type="general", dose=doses, resp=est, S=as.matrix(C),
models=candMod, Delta=3, alpha=0.05)
```

Repeated measurements (e.g., changes from baseline to Weeks 2, 4 and 8) will be analyzed in two ways: focusing on the last time point (e.g., Week 8 and using Week 2 and Week 4 only to predict missing data, if needed) and estimating the average effect over time. In both cases the general MCP-Mod approach was used.

Last time point. First a mixed model is fitted with factors for treatment group, time and treatment by time interaction and covariates for the baseline value and the interaction between baseline and time. An unstructured covariance matrix will be used to account for the correlation between repeated measurements from the same subject. The SAS statements for this model are:

```
ods output lsmmeans=lsm1 (where=(week=8)); * export data set lsm1 as xpt file;
proc mixed data=dset noclprint=6;
  class treat week subjid;
  model outcome=treat week treat*week base base*week;
  repeated week/ subject=subjid type=un;
  lsmmeans treat*week/ cov;
  where treat in (0,1,2,3,4);
run;
```

The LSMeans at Week 8 will then be analyzed using the general MCP-Mod approach. The R statements for this analysis are the same as above, except for:

```
C <- lsm[,c("COV3","COV6","COV9","COV12","COV15")] # covariance matrix
```

Average over time. First the same mixed model is fitted, but without the treatment by time interaction. The SAS statements for this model are:

```
ods output lsmeans=lsn2; * export data set lsn2 as xpt file;
proc mixed data=dset noclprint=6;
  class treat week subjid;
  model outcome=treat week base base*week;
  repeated week/ subject=subjid type=un;
  lsmeans treat/ cov;
  where treat in (0,1,2,3,4);
run;
```

Then the LSMeans (averages over time) will be analyzed using the same R statements as above with:

```
C <- lsm[,c("COV1","COV2","COV3","COV4","COV5")] # covariance matrix
```

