10 STATISTICAL ANALYSES

10.1 Overall testing strategy

All statistical testing will be performed at a two-sided significance level of 0.05 using 95% confidence intervals (CIs).

In the main analysis of the primary endpoint in the PPS the type I error is controlled by the MCT part of the MCP-Mod methodology. The primary objective of the trial will be evaluated based on this analysis.

The type I error of the MCP-Mod analysis in the FAS is similarly protected. In the other supportive analysis of the primary endpoint Dunnett's test will be used to correct for testing multiple doses vs placebo. The alpha is formally controlled only for the main analysis; all other analyses are considered exploratory.

In all analyses of secondary and other efficacy variables, no correction will be made for multiple testing.

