10.6.3 Main analysis

The change from baseline to Week 8 of DB treatment period (Period II) in mean trough SiDBP will be analyzed using the MCP-Mod approach [Bretz 2005, Pinheiro 2006] described in Section 9.1.

A placebo-corrected mean reduction from baseline of at least 4 mmHg is considered clinically relevant.

Some examples of E_{\max} dose-response relationships are given in Figure 3, where it is assumed that the minimum response will be obtained with placebo (mean change from baseline -4 mmHg) and the maximum response (change from baseline -8 or -9 mmHg) will be reached at the highest dose of ACT-132577 (50 mg).

Figure 3 **Examples of E_{\max} dose-response relationships**

Six candidate dose-response models were pre-specified in the protocol: linear, linear in log-dose, quadratic, E_{\max} , sigmoidal E_{\max} and logistic. The analysis will be performed using the R-package *DoseFinding* [Bornkamp 2016]. A dose-response relationship is demonstrated if at least one of the six MCTs has an adjusted p-value < 0.05. The best fitting model will be selected based on AIC. That model will be used to estimate the minimum effective dose, defined as the dose that achieves a placebo-corrected mean reduction from baseline of at least 4 mmHg with a 95% CI excluding 0.

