1 INTRODUCTION

This Statistical Analysis Plan (SAP) describes statistical analyses required for the blinded sample size re-estimation (SSR) of Study AC-080A201, the Phase 2 dose-finding trial of the ACT-132577 project.

The objective is to provide the sizes of the Per-Protocol Set (PPS) and Full Analysis Set (FAS) which, given the observed variability at this point in time, will guarantee approximately 90% power to detect a dose response relationship and provide sufficient precision in the estimation of the dose response curve and of doses that will be selected for the Phase 3 program of ACT-132577.

The blinded SSR will be performed by the sponsor after 100 subjects have been randomized and their Week 8 blood pressure (BP) data are available for analysis. The sample size will be recalculated considering the overall standard deviation (SD) of the primary endpoint (change from baseline to Week 8 in mean trough sitting diastolic blood pressure [SiDBP], measured by automated office blood pressure measurement [OBPM]) in the Per-Protocol Set.

The re-calculated size of the PPS is expected to be between 280 subjects and the originally foreseen 420 subjects. The associated number of subjects to be randomized will also be re-estimated and is expected to be between 300 subjects and the originally planned 540 subjects. It is anticipated that the size of the PPS will be at least 80% of the size of the FAS.

This SAP is based on Version 3 of the Protocol dated 30 May 2016 [D-16.063].

Version 2 of this SAP was generated in order to make editorial corrections—no changes were made to analyses or statistical content—and to reflect the transfer of ownership of ACT-132577. ACT-132577 was previously developed by Actelion Pharmaceuticals Ltd. Actelion was recently acquired by Johnson & Johnson. As part of this transaction, Actelion spun off its drug discovery operations and early stage clinical development assets into an independent biopharmaceutical company, Idorsia Pharmaceuticals Ltd (Idorsia). ACT-132577 is now owned by Idorsia.

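### The SAP defines the minimum effective dose at a 4 mmHg placebo-corrected reduction, but its MCP-Mod code targets 3 mmHg, so the dose it returns falls short of the SAP's own clinically relevant effect.

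*SAP*

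**What the plan says.** Two parts of the SAP give different targets for diastolic pressure.

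- **Definition.** SAP 10.6.3 derives the minimum effective dose from the AIC-selected model. It is there "defined as the dose that achieves a placebo-corrected mean reduction from baseline of at least 4 mmHg with a 95% CI excluding 0". Protocol 11.3.2.3 gives the same definition. SAP 10.6.3 adds the reason for the figure: "A placebo-corrected mean reduction from baseline of at least 4 mmHg is considered clinically relevant".
- **Code.** The primary-endpoint MCPMod call in SAP 9.2 ends with "candMod, Delta=3", and the text below it explains that "Delta is a target difference vs placebo (Delta=3 for DBP; Delta=5 for SBP". The fitted object "will be summarized to obtain the MCP test, parameter estimates, target dose and AIC", and these go into a summary table. SAP 9.3 repeats the value in its text and in the general MCP-Mod call ("models=candMod, Delta=3, alpha=0.05").

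The opening of SAP section 9 says the programming statements are there to fix the analysis details. SAP 4.1, which records departures from the protocol, mentions no move from 4 to 3 mmHg. Neither document gives a reason for 3 mmHg. None of the outputs listed in SAP 13.6 is titled minimum effective dose.

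**The concern.** Protocol 1.3 and 3.2 state that the trial is meant to select doses for Phase 3, and the minimum effective dose is the one quantity in the main analysis that turns the fitted curve into a dose. The only coded dose estimate solves for 3 mmHg. A programmer who follows section 9 delivers that dose; a statistician who follows 10.6.3 delivers a different one. Both could claim to have followed the plan, and the choice between them could be made with the data in view.

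The second half of the definition, a 95% CI that excludes 0, has no code at all.

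**Working it through.** **1. What Delta does.** A dose solved for Delta=3 has a fitted placebo-corrected effect of 3 mmHg by construction. The shortfall against the definition is (4 − 3)/4 = 25%. Delta does not enter the contrast test, the model fits or AIC.

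**2. Check that the planning curves are read correctly.** The power program in the sample size re-estimation SAP (appendix 15.2) gives four sigmoid Emax curves by ED50 and ED90. Expressed in mg, with Hill coefficient h = ln 9 / (ln ED90 − ln ED50) rounded to two decimals as in the program:

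| Scenario | ED50 / ED90 (mg) | h | Maximum effect (mmHg) |
|---|---|---|---|
| 1 | 12.5 / 25 | 3.17 | 4.9 (5 in the program) |
| 2 | 12.5 / 50 | 1.58 | 4.5 |
| 3 | 25 / 50 | 3.17 | 4.5 |
| 4 | 25 / 75 | 2.00 | 4.0 |

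The maxima are those of protocol Table 2. Protocol Table 4 states 63 subjects per group for 90% average power at SD 9. A simulation of the two-sided 0.05 multiple contrast test with the six candidate models, taking the maximum as reached at 50 mg and using the program's 5 mmHg for scenario 1, gives 90.2%. At 47 per group it gives 80.6% (stated 80%), and at 79 per group 95.2% (stated 95%). Reading the maximum as the asymptote instead gives 81.9% at 63 per group, which does not match. The curves are therefore scaled to reach their maximum at 50 mg.

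**3. Dose for 3 and for 4 mmHg on the planning curves.** With f(d) = A·d^h / (ED50^h + d^h) and A chosen so that f(50) equals the maximum, the dose for effect D is

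d = ED50 · [D / (A − D)]^(1/h).

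Scenario 4 as an example: 50²/(25² + 50²) = 0.80, so A = 4.0/0.80 = 5.0. For D = 3, d = 25·√(3/2) = 30.6 mg. For D = 4, d = 25·√(4/1) = 50.0 mg.

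| Scenario | Dose for 3 mmHg (mg) | Dose for 4 mmHg (mg) | Reduction |
|---|---|---|---|
| 1 (maximum 4.9) | 14.3 | 19.6 | 27% |
| 2 | 16.1 | 30.0 | 46% |
| 3 | 28.4 | 38.7 | 27% |
| 4 | 30.6 | 50.0 | 39% |

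With the program's 5 mmHg maximum, scenario 1 becomes 14.1 against 19.0 mg. In scenario 2 the two answers lie on opposite sides of the studied 25 mg dose.

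**4. The six candidate shapes.** These use the starting values in SAP Table 3 and an assumed effect of 4.5 mmHg at 50 mg. For the Emax shape with ED50 = 50, f(d) = 9d/(50 + d). Setting f = 3 gives d = 150/6 = 25 mg, and f = 4 gives d = 200/5 = 40 mg.

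| Shape | 3 mmHg (mg) | 4 mmHg (mg) | Reduction |
|---|---|---|---|
| Linear | 33.3 | 44.4 | 25% |
| Linear in log | 10.3 | 29.7 | 65% |
| Quadratic | 29.3 | 42.3 | 31% |
| Emax | 25.0 | 40.0 | 38% |
| Sigmoid Emax | 12.5 | 32.0 | 61% |
| Logistic | 34.5 | 44.9 | 23% |

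With 5 mmHg assumed at 50 mg the range is 23–62%.

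**5. A weaker drug.** If the effect at 50 mg is assumed to be 3.5 mmHg, Delta=3 still returns a dose on every candidate shape (25.6 to 43.4 mg), while no dose in the studied range reaches 4 mmHg.

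The doses in steps 3 to 5 only show how far the target moves the answer. They say nothing about which dose is right.

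**The case against.** The best case for the plan is that the code never claims to return the minimum effective dose. It returns a target dose for an openly stated difference, while 10.6.3 separately requires a dose at 4 mmHg with its CI condition. A careful analyst would still have to derive that. This is possible, and it makes the consequence conditional on the code being run as written. But the SAP never says the two terms mean different things, and it neither codes nor lists the 4 mmHg dose.

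Four further points deserve weight.

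- The primary inference is untouched. The objective is judged by the contrast test, so type I error, power, sample size, model choice and the fitted curve do not change. This stands and limits the finding to the dose estimate.
- Readers will also see the best-fitting curve and the ANCOVA comparison of each studied dose with placebo, with confidence limits. These would let a reader compare the studied doses with 4 mmHg. They lessen the risk of a wrong Phase 3 choice but do not supply the defined quantity.
- In three of the four planning scenarios both answers stay between the same neighbouring studied doses (50.0 mg in scenario 4 being the upper end). The candidate shapes use starting values that are re-estimated from the data. Both points are true, so the sizes above are a range and not a forecast.
- The minimum effective dose is defined only for the main analysis, whereas SAP 9.3 covers other endpoints, repeated-measures sensitivity analyses and the average over time. Strictly, then, the contradiction is in 9.2. The reason to align 9.3 is that a sensitivity analysis aimed at another target cannot be compared with the main one.

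**Conclusion.** The concern holds. Both documents define the minimum effective dose at 4 mmHg, the code solves for 3 mmHg, and no explanation or recorded change connects them. The coded dose has a fitted effect 25% below the SAP's relevance threshold. It is 27–46% lower than the 4 mmHg dose on the sponsor's planning curves, and 23–65% lower on the candidate shapes if the effect at 50 mg is 4.5 mmHg.

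The contradiction and the 25% shortfall need no assumption about the true curve. The size of the shift in mg does: it depends on the curve and on the effect at 50 mg. The finding also assumes that the coded target dose is what gets reported, which is what SAP 9.2 says goes into the summary table. It must be fixed because it touches the one estimate meant to carry the result into dose selection.

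**What to change.** - Set Delta=4 in every diastolic MCPMod call in SAP 9.2 and 9.3, so that the code returns the quantity that both documents define.
- Add a step that computes the 95% CI of the modelled difference from placebo at that dose and applies the condition that it excludes 0.
- State in SAP 9.2 that the target dose for diastolic pressure is the minimum effective dose of 10.6.3, and list it as an output in SAP 13.6. Say what is reported when no dose from 0 to 50 mg qualifies.
- If 3 mmHg is wanted as an additional target, label it separately, give the reason in SAP section 4, and do not call it the minimum effective dose.

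The cost is one argument in the R code, one extra confidence interval, one output line and a few sentences, all settled before unblinding. The price in results is that the reported dose may be higher, or may not exist within the studied range.
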